1. AMENDMENTS FROM PREVIOUS VERSION(S)

To be completed for any changes made post-finalisation

2. TABLE OF ABBREVIATIONS

Abbreviation	Definition
ALL	Acute Lymphoblastic Leukaemia
CR	Complete Remission
InO	Inotuzumab Ozogamicin
MRD	Minimal Residual Disease
VOD	Veno-occlusive Disease
SOS	Sinusoidal Obstruction Syndrome
TRAE	Treatment Related Adverse Event
HSCT	Hematopoietic Stem Cell Transplant
EMA	European Medical Agency
UK	United Kingdom
NICE	National Institute for Health and Care Excellence
CUP	Compassionate Use Program
NHS	National Health Service
SAP	Statistical Analysis plan
CRi	Complete Remission with incomplete hematological recovery
OS	Overall Survival
RFS	Relapse-free Survival
NRM	Non-relapse Mortality
CAR	Chimeric Antigen Receptor
ECOG	Eastern Cooperative Oncology Group
ANC	Absolute Neutrophil Counts
ALT	Alanine Transaminase (also known as alanine aminotransferase)
AST	Aspartate Transaminase (also known as aspartate aminotransferase)
ALP	Alkaline Phosphatase
GGT	Gamma-Glutamyl Transferase
CCI	CCI
eCRF	Electronic Case Report Form
MLL	Mixed Lineage Leukaemia
IQR	Interquartile range
CI	Confidence Interval
AE	Adverse Event
NI	Non-Interventional

3. INTRODUCTION

Note: in this document any text taken directly from the non-interventional (NI) study protocol is *italicised*.

Inotuzumab ozogamicin (InO) is a CD22 monoclonal antibody that was shown to improve outcomes of patients with relapsed/refractory B-cell acute lymphoblastic leukaemia (ALL) or Philadelphia chromosome positive ALL. In the phase III INO-VATE ALL study, patients receiving InO versus standard chemotherapy achieved significantly higher complete remission (CR) rates and minimal residual disease (MRD)-negativity rates. Veno-occlusive disease (VOD)/sinusoidal obstruction syndrome (SOS) was reported in INO-VATE ALL as a treatment related adverse event (TRAE), on average two weeks after end of treatment with InO, and especially in patients who had follow-up hematopoietic stem cell transplant (HSCT) therapy.

InO was approved by the European Medicines Agency (EMA) in June 2017. InO recently gained recommendation from the National Institute for Health and Care Excellence (NICE) in the United Kingdom (UK) in line with the licensed indication on 9th August 2018 and is now available in routine care practice throughout the UK. Prior to NICE approval, InO was made available to UK patients through a compassionate use program (CUP) run by Pfizer Inc. between June 2016 and October 2017, and via private purchase. As part of the CUP alone, approximately 75 patients were treated across 31 National Health Service (NHS) Trusts, each Trust treating between 1 and 15 patients. Patient level data is available in medical records, enabling a retrospective chart review to be conducted.

There is a paucity of information on clinical outcomes in UK patients with relapsed/refractory B-cell ALL treated with InO outside of the context of clinical trials. The number of patients enrolled in INO-VATE ALL from the UK was limited. In this context, a retrospective chart review evaluating real world effectiveness and safety of InO for ALL when administered in routine care in the UK is of interest to clinicians and patients.

3.1. Study Design

This is a UK, multi-centre, retrospective, non-interventional cohort study based on secondary use of hospital medical records (paper-based and/or electronic, as appropriate). Three to five out of the 31 NHS Trusts that treated the largest number of patients with InO as part of the CUP will be initially selected for this study (the number of centres may be further expanded). A retrospective design has been selected as data have already been recorded into medical records and are available for data collection. The study is non-interventional as all patients received InO as part of routine clinical care, either via enrolment into the CUP or via private purchase.

3.1.1. Key Definitions

- *Index date: the date of initiation of the first cycle of InO.*

[figure not shown]
- *Baseline period: period from 6 months prior to index date. The closest observation recorded during the baseline period to the index date will be used as baseline data (when more than one observation is available).*
- *Pre-index observation period: period from the date of ALL diagnosis to the index date.*
- *Post-index observation period: period from the index date until the date of death, or date of latest visit at the time of data collection, whichever is soonest.*
- *CR/CRi rate: number of patients who achieve CR/CRi divided by the total number of patients completing treatment with InO (defined as patients with a recorded date of discontinuation of InO).*
- *MRD negativity rate: proportion of patients in whom MRD-negative status is observed, among patients in whom MRD negativity status has been assessed, at any time until the end of treatment with InO (defined as the date of recorded discontinuation of InO).*
- *OS: time from index date to death.*
- *RFS (interchangeable with EFS for the purpose of this SAP): time from index date to the earliest date of the following events: death, progressive disease (including objective progression, relapse from CR/CRi, treatment discontinuation due to global deterioration of health status) and start of new induction therapy or posttherapy HSCT without achieving CR/CRi.*
- *NRM: Time from the date of follow-up HSCT until death without disease progression or relapse. Deaths from any cause without prior progression are events. Events related to the disease such as relapse, progression are competing events, loss of follow-up are censored.*

Patients will be observed from the start of the pre-index observation period until the end of the post-index observation period. For the purpose of identifying risk factors for VOD/SOS and replicating the findings by Kantarjian et al¹ follow-up will be defined as the post-index observation period, and patients will be censored at the date of the last recorded clinic visit prior to data collection.

For the estimation of endpoints, the following definitions will be implemented. The index date will be defined as the date of initiation of the first cycle of InO. CR/CRi rate will be defined as the number of patients who achieve CR/CRi divided by the total number of patients completing treatment with InO (defined as patients with a recorded date of discontinuation of InO). The MRD negativity rate will be defined as the proportion of patients in whom MRD-negative status is observed, among patients in whom MRD negativity status has been assessed, at any time until the end of treatment with InO (defined as the date of recorded discontinuation of InO). OS will be defined as the time from index date to death,

RFS will be defined as the time from index date to the earliest date of the following events: death, progressive disease (including objective progression, relapse from CR/CRi, treatment discontinuation due to global deterioration of health status), and start of new induction therapy or post-therapy HSCT without achieving CR/CRi. NRM will be defined as the time from date of follow-up HSCT until death without disease progression or relapse. Deaths from any cause without prior progression are events. Events related to the disease such as relapse or progression are competing events. Patients who are lost to follow-up will be censored at the last known visit date. Patients who are still alive at the study cut-off date (31st December 2020) or the last visit date available will be censored (at whichever occurred first).

Figure 1. Study design and observation periods

The baseline period is 6 months prior to the index date. All other time periods shown are variable for each patient.

3.1.2. Study Population

The source population for this study is adult patients treated with InO at the selected sites and who accessed InO via NHS commissioning, via the CUP or via private purchase between June 2016 and date of data collection (December 31st 2020). The NICE recommendation is as an option for treating relapsed or refractory CD22-positive B-cell precursor acute lymphoblastic leukaemia in adults; and patients with relapsed or refractory Philadelphia chromosome positive disease should have had at least 1 tyrosine kinase inhibitor. The eligibility criteria for inclusion into the CUP is provided in Section 16 Annex 1 of the study protocol.

Patients will be eligible for inclusion in the present study if they fulfil all the following criteria:

Inclusion Criteria

- *Patients with relapsed/refractory ALL.*
- *Patients who initiated InO between 1st of June 2016 and date of data collection (to be confirmed).*

- *Patients who accessed InO treatment via NHS commissioning, via the CUP, or via private purchase.*
- *Patients aged ≥ 18 years old at initiation of InO treatment.*

Exclusion Criteria

- *Patients initiated on treatment with InO at a different hospital than the ones selected in this study.*
- *Patients with < 3 months of follow-up since index date, unless death occurs < 3 months from index date.*

Consent will not be required as all identifiable patient data (from surviving and deceased patients) will be extracted by the patient's direct medical care team. Eligible patients will be selected by chronological order and with a priority given to patients treated via NHS commissioning, where possible.

3.1.3. Data Source

Data for this study will be initially collected through retrospective data collection from three to five NHS Trust cancer services in the UK which were part of the CUP (additional centres may be added at a later stage if the target sample size is not achieved). The sample size of approximately 25 patients has been based on the number of patients expected to be available at three centres that individually treated the largest number of patients with InO. Further detail regarding sample size can be found in section 9.5 of the study protocol.

Data on patient demographic and clinical characteristics, treatment patterns, outcomes, and AEs will be collected from paper based and/or electronic hospital medical records (as applicable at each site) by members of the patient's direct care team in anonymised-coded form.

Data will be collected using anonymized-coded eCRFs designed specifically for the study. Participants will be identified in all study records by a unique participant identification number to allow data management queries to be resolved with reference to source medical records while preserving patient confidentiality.

4. STUDY OBJECTIVES

The purpose of this study is to describe the demographics and clinical characteristics, treatment pathway, and effectiveness and safety of InO in patients with relapsed/refractory B-cell ALL treated with InO in the real-world.

The objectives of the study are as follows.

Primary Objective:

- To describe the baseline demographic, clinical (including previous treatment) and laboratory characteristics of patients with relapsed/refractory B-cell ALL at initiation of treatment with InO.

Secondary Objectives:

- To describe the InO treatment pathway, including InO doses, dose modifications and number of cycles of treatment; and concomitant medications.
- To summarise CR or CR with incomplete haematological recovery (CR/CRi) rates at completion of treatment with InO, overall and stratified according to the number of salvage therapies (0, 1, ≥ 2) received prior to InO initiation.
- To summarise MRD negativity rates in patients assessed for MRD negativity, at completion of treatment with InO, and describe the number of cycles of InO needed to attain MRD negativity.
- To describe overall survival (OS), and cause of death; in all patients with or without subsequent HSCT.
- To describe overall HSCT rate and rate in patients going directly into HSCT (eg, without another induction therapy).
- To describe RFS; in all patients and in patients with or without follow-up HSCT. Additionally, to describe non-relapse mortality (NRM) in patients undergoing follow-up HSCT.
- To describe the treatments for ALL and responses to treatment post InO, including HSCT, chemotherapy regimens and chimeric antigen receptor T-cell therapy.
- To describe the occurrence of safety events including documented diagnoses of VOD/SOS, grade 3/4 TRAEs (lung/cardiac/kidney) and other liver dysfunction following InO initiation; in all patients and in patients with or without follow-up HSCT. In addition, to evaluate associations between risk factors identified in the INO-VATE ALL trial (pre-HSCT AST or ALT level \geq ULN, pre-HSCT bilirubin \geq ULN, use of dual-alkylating agents as transplant conditioning).and risk for VOD/SOS in patients with follow-up HSCT.

5. INTERIM ANALYSES

According to the study protocol, there are currently no interim analyses planned for this study.

6. HYPOTHESES AND DECISION RULES

6.1. Statistical Hypotheses

This is a descriptive study and there is no a priori hypothesis specified.

6.2. Statistical Decision Rules

N/A

7. ANALYSIS SETS/POPULATIONS

*The source population for this study is adult patients treated with InO at the selected sites and who accessed InO via NHS commissioning, via the CUP or via private purchase between June 2016 and February 2019. The NICE recommendation is as an option for treating relapsed or refractory CD22- positive B-cell precursor ALL in adults; and patients with relapsed or refractory Philadelphia chromosome positive disease should have had at least 1 tyrosine kinase inhibitor9 (see **Annex 1** of the protocol for NICE eligibility criteria). The eligibility criteria for inclusion in the CUP are provided in Annex 1 of the protocol.*

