6. MILESTONES

Milestone	Planned date
Start of data collection	01 September 2019
End of data collection	15 January 2020
Final study report	01 March 2020

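### The SAP gives two end dates for the cohort, February 2019 and 31 December 2020, and the 3-month follow-up rule keeps early deaths while dropping survivors with short follow-up

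*SAP*

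**What the plan says.** - **SAP 7 (Analysis Sets/Populations)** describes the source population as adults who accessed InO through NHS commissioning, the CUP or private purchase "between June 2016 and February 2019". Protocol 9.2.1 gives the same end date.
- **SAP 3.1.2 (Study Population)** describes the same source population but runs it "between June 2016 and date of data collection (December 31st 2020"). Its inclusion criterion leaves the end open: "Patients who initiated InO between 1st of June 2016 and date of data collection (to be confirmed"). The inclusion criteria in Protocol 4 and 9.2.1 also run to the date of data collection, so Protocol 9.2.1 carries both an open criterion and a February 2019 source population.
- **SAP 3.1.1 (Key Definitions)** uses the same December date for censoring: "Patients who are still alive at the study cut-off date (31st December 2020) or the last visit date available will be censored", whichever comes first. It ends a survivor's observation at the latest visit available when data are collected.
- **Exclusion criterion, SAP 3.1.2 and Protocol 9.2.1:** patients with under 3 "months of follow-up since index date, unless death occurs" within those 3 months.
- **Full analysis set, SAP 7.1:** all eligible enrolled patients, so it inherits whichever window applies.

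**The concern.** The window decides who is analysed. The primary objective is a description of baseline characteristics, so it depends directly on cohort membership. An analyst working from SAP 7 and one working from SAP 3.1.2 could build different datasets. Protocol 9.9 itself names access route as a possible source of selection bias, and the access routes were open at different times.

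The follow-up rule adds a second problem because it selects on outcome. A patient who dies within 3 months is kept however short the follow-up. A patient who is alive but was last seen before 3 months is removed. When the end of initiation and the censoring date are the same day, every late starter faces that asymmetry. It pushes OS and RFS downward, most visibly at the 3-month landmark.

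**Working it through.** **Is there a precedence rule?** Protocol 9.7 lets the SAP modify the protocol's plans, but here the SAP disagrees with itself. When the SAP means to override a definition it says so, as SAP 10.2.4 does for the MRD denominator. It says nothing similar about the window, and neither document records an amendment that would settle it.

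**Length of the two windows** (30.4375 days per month, both ends included)
- 1 June 2016 to 28 February 2019: 1,003 days / 30.4375 = 33.0 months.
- 1 June 2016 to 31 December 2020: 1,675 / 30.4375 = 55.0 months.
- Difference: 672 / 30.4375 = 22.1 months.

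**Who can meet the 3-month rule by 31 December 2020?** From 1 October to 31 December 2020 is 91 days, and three calendar months from 1 October end on 1 January 2021. The last start date that allows 3 months is therefore 30 September 2020. Anyone starting later is excluded if alive at the cut-off and included if dead. If initiation closes in February 2019, everyone has at least about 22.1 months of potential follow-up and this route disappears.

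**Size of the last-quarter part.** The plan states no figure to reproduce. Assumptions: uniform accrual over the window, and exponential survival with the 7.7-month median OS (95% CI 6.0 to 9.2) that Protocol 7 cites for InO in the phase III trial.
- Share of starters in the last quarter: 92 / 1,675 = 5.5%.
- Mean probability of death before the cut-off for those starters: 1 − (1 − e^(−λQ)) / (λQ), with λ = ln 2 / 7.7 = 0.0900 and Q = 92 / 30.4375 = 3.02 months. This gives 12.4% (15.6% at a median of 6.0 months, 10.6% at 9.2).
- Share of included patients who are such deaths: 0.0549 × 0.1245 / (0.9451 + 0.0549 × 0.1245) = 0.7%, or 0.18 of 25 patients.

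Kaplan-Meier estimates from 1,000,000 simulated patients, without and with the rule:

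| Assumed median | Accrual | 3-month survival | Median OS (months) |
|---|---|---|---|
| 6.0 | June 2016 on | 70.7% → 70.1% | 5.99 → 5.92 |
| 6.0 | August 2018 on | 70.8% → 69.5% | 6.01 → 5.86 |
| 7.7 | June 2016 on | 76.3% → 75.8% | 7.70 → 7.62 |
| 7.7 | August 2018 on | 76.4% → 75.3% | 7.69 → 7.53 |
| 9.2 | June 2016 on | 79.8% → 79.3% | 9.20 → 9.12 |
| 9.2 | August 2018 on | 79.8% → 78.8% | 9.20 → 9.04 |

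The August 2018 rows represent a cohort made up only of patients starting after the NICE recommendation.

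**Survivors last seen early, at any calendar time.** This route exists under either end date. The documents give no rate of early loss, so only the size per patient can be shown. With 25 patients and 76.3% survival, expected deaths by 3 months are 25 × 0.237 = 5.9, say 6. Suppose one of the 19 survivors is last seen just before 3 months. Censoring that patient gives 19/25 = 76.0%; excluding the patient gives 18/24 = 75.0%. Each such exclusion costs up to about 1 point.

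**The case against.** The strongest reply is that February 2019 is a leftover. SAP 3 says that italics mark text taken from the protocol, and the SAP 7 paragraph is italicised. Every inclusion criterion runs to the date of data collection, and SAP 3.1.1 and 3.1.2 both give 31 December 2020. This makes the later date the more likely intention, so the two windows are not equally plausible. It does not settle the matter, because the superseded date still stands in the section headed analysis sets and no text withdraws it.

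The second reply is that the last-quarter effect is small and conditional. That stands. Selection is chronological towards about 25 patients, so the places may fill before October 2020. Priority for NHS-commissioned patients could work the other way, and the documents give no accrual pattern.

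Three stronger readings are tempting but not supported:
- The protocol milestone of "15 January 2020" might look like a third window. It is a planned date for ending data collection and does not define eligibility.
- A reader might infer that a February 2019 end leaves little NHS-commissioned experience. The documents give no patient counts by access route. The 22-month gap is calendar time, not patients.
- A reader might take the 12% who enter and the 88% who do not as the bias in OS. Those figures describe last-quarter starters only.

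**Conclusion.** The date conflict is real, sits in current text and needs reconciling: 33 against 55 months, with no statement of which governs. How many patients it moves cannot be derived from the documents.

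The follow-up rule selects on outcome, and the direction is downward for OS and RFS. Its last-quarter part applies only if 31 December 2020 governs. At a 7.7-month median it is worth about 0.5 to 1 point on 3-month survival and 0.1 to 0.2 months on median OS, and it may be nil. Over the cited confidence limits for the median, the 3-month effect runs from about 0.5 to 1.3 points. These figures rest on uniform accrual and exponential survival, and RFS was not modelled. The part due to earlier starters last seen before 3 months applies under either date, and its total cannot be sized without a rate of early loss.

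**What to change.** 1. State one InO initiation end date in identical words in Protocol 9.2.1, SAP 3.1.2 and SAP 7. Delete the superseded date, and remove the placeholder from the SAP 3.1.2 criterion and from Protocol 4.
2. Set that date at least 3 months before the follow-up cut-off. For a cut-off of 31 December 2020 this means no later than 30 September 2020. February 2019 also satisfies it, if that was the intention. The choice is the sponsor's.
3. Define the 3-month rule by potential follow-up (index date to cut-off), not observed follow-up. Censor survivors last seen before 3 months at their last visit instead of excluding them. Closing initiation early does not by itself remove this second route.

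The cost is wording in both documents. Any patients starting in the last quarter are not included, and a few survivors with short follow-up enter as censored observations.

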7.1. Full Analysis Set

The full analysis set will be comprised of medical records extracted for the purpose of the study from all eligible patients who are enrolled into the study.

7.2. Safety Analysis Set

The safety analysis set will be comprised of medical records extracted for the purpose of the study from all eligible patients who are enrolled into the study and have at least one dose of study medication.

7.3. Subgroups

Where sample size allows ($n > 5$), the following endpoints will be analysed overall and separately for the subgroups stated below. The analyses will follow the methods described in [Section 10.1](#). More detail on the criteria for each subgroup can be found in [Section 9](#) where applicable.

Outcome	Supports Protocol Objective Number	Subgroups
CR, CRi and CR/CRi response rates by the end of InO treatment	Secondary Objective 2	Overall, and by number of salvage therapies in the pre-index observation period (0,1, ≥ 2).
Number and proportion of patients achieving MRD negativity	Secondary Objective 3	Overall, and by number of completed cycles of InO and by number of salvage therapies in the pre-index observation period (0,1, ≥ 2).
Number and proportion of patients surviving at 3,6 and 12 months after InO initiation	Secondary Objective 4	Overall, and separately in patients with and without follow-up HSCT and by number of salvage therapies in the pre-index observation period (0,1, ≥ 2).

Outcome	Supports Protocol Objective Number	Subgroups
Cause of death	Secondary Objective 4	Overall, and separately in patients with and without follow-up HSCT.
Median OS (95% CI)	Secondary Objective 4	Overall, and separately in patients with and without follow-up HSCT.
Proportion of patients who are relapse free at 3, 6 and 12 months after InO initiation	Secondary Objective 5	All patients, separately in patients with follow-up HSCT.
Median RFS (95% CI)	Secondary Objective 5	All patients, separately in patients with follow-up HSCT.
Proportion of patients initiated on each treatment	Secondary Objective 6	Per treatment (chemotherapy (blinatumomab, other). HSCT, CAR T-cell therapy).
Response to treatment	Secondary Objective 6	Overall, and per treatment (chemotherapy (blinatumomab, other). HSCT, CAR T-cell therapy).
Survival following treatment	Secondary Objective 6	Per treatment (chemotherapy (blinatumomab, other). HSCT, CAR T-cell therapy).
Number and proportion of patients experiencing VOD/SOS during the post-index observation period	Secondary Objective 7	All patients, and in the following subgroups: no HSCT prior to InO, at least 1 HSCT prior to InO, no post-InO HSCT and patients with at least 1 HSCT post-InO. Patients will be assigned to one of these 4 groups which will be analysed separately. For each group, grade of VOD/SOS and follow-up treatment (Follow-up chemotherapy after completion of chemotherapy and follow-up HSCT after HSCT) will be presented.
Treatments received for VOD/SOS	Secondary Objective 7	All patients, separately in patients with follow-up HSCT.
Survival following treatment	Secondary Objective 7	All patients, separately in patients with follow-up HSCT.
Number and proportion of patients experiencing grade 3 or 4 TRAEs	Secondary Objective 7	All patients, separately in patients with follow-up HSCT.
Treatments received for grade 3 or 4 TRAE	Secondary Objective 7	All patients, separately in patients with follow-up HSCT.
InO dose delay as a result of grade 3 or 4 TRAE	Secondary Objective 7	All patients, separately in patients with follow-up HSCT.
Number and proportion of patients experiencing other liver dysfunctions (all grades)	Secondary Objective 7	All patients, separately in patients with follow-up HSCT.
Treatments received for other liver dysfunction	Secondary Objective 7	All patients, separately in patients with follow-up HSCT.
InO dose delay as a result of other liver dysfunction	Secondary Objective 7	All patients, separately in patients with follow-up HSCT.
Peripheral blood blast counts prior to follow-up HSCT	Secondary Objective 7	All patients, separately in patients with follow-up HSCT.

PFIZER CONFIDENTIAL

Outcome	Supports Protocol Objective Number	Subgroups
Number and proportion of patients with significant risk factors for VOD/SOS	Secondary Objective 7	Where patient numbers allow, all patients, separately in patients with follow-up HSCT.

